### **2.2 Secondary outcome measures**

The following secondary clinical outcomes will also be assessed:

1. OI at days 4 and 14
2. Physiological indices of ARDS, as measured by respiratory compliance (CRs) and P/F ratio on days 4, 7 and 14
3. Organ failure as measured by change in sequential organ failure assessment (SOFA) score from baseline to days 4, 7 and 14
4. Safety and tolerability as assessed by the occurrence of adverse events/reactions (AE/AR), serious adverse events/reactions (SAE/SAR) and suspected unexpected serious adverse reactions (SUSAR).

Outcomes will be measured at baseline and daily up to day 14 or until the patient is discharged from ICU or the patient dies. Although duration of ventilation, ventilation free days at day 28 and 28 and 90-day mortality as well as length of ICU stay will be recorded, these important clinical outcomes are not included as major outcome measures as the study is not adequately powered to assess these outcomes.

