### 3.4 Data verification

Data verification, consistency and range checks will have been performed at the data entry stage by the CTU, as well as checks for missing data (copies can be found in the Trial Master File). Additional range, consistency and missing data checks will be performed, as appropriate, when the analysis is performed (and when the datasets for analysis are constructed). All variables will be examined for unusual, outlying, unlabelled or inconsistent values.

Given the thorough nature of our follow-up procedure we expect the issue of missing data to be relatively minimal. We anticipate high compliance with initial data collection as this is close to the time of patient registration. If any data is missing imputation will not be done.

Any problems with trial data will be queried with the Trial Managers, Data Managers, or statisticians, as appropriate. If possible, data queries will be resolved, although it is accepted that due to administrative reasons and data availability a small number of problems will continue to exist. This will be minimised.

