## 5. SAMPLE SIZE CALCULATIONS

The primary outcome measure is the difference in OI at day 7, between aspirin and placebo treated groups. Based on our data from a recently completed clinical trial in ARDS, the mean (standard deviation; SD) OI at day 7 in patients with ARDS is 62 (51) cmH2O/kPa. A sample size of 56 subjects (28 in each group) will have 80% power at a two-tailed significance level of 0.05 to detect a clinically significant difference of 39 cmH2O/kPa in OI between groups. In a previous phase 2 study of similar size, we have found that an intervention can demonstrate a change in OI of a similar magnitude confirming a treatment effect of this size can be achieved.

Although we anticipate few withdrawals or loss to follow-up we have allowed for this in the sample size calculation. In our previous single centre study of simvastatin in ARDS there were no withdrawals. In a multi-centre UK study of pulmonary artery catheters in ICU patients

(PAC-Man), no patients were lost to follow up, and only 3% withdrew consent after recovering competency. This is in keeping with our local data. Therefore, a drop-out rate of 5% has been estimated and the study will require a total of 60 patients (30 in each group). All calculations assume 80% power at a two-tailed significance level of 0.05.

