## 6. ANALYSIS PRINCIPLES

Primary outcome measure is the OI at day 7. Unadjusted (primary analysis) and adjusted analysis will be carried out to test whether there is a statistically significant difference between the aspirin & placebo groups. Secondary analysis will be carried out, if the day 7 OI values are missing, using last value carry forward method.

Secondary outcome measures are OI, CRs, PF ratio, and SOFA score at day 4, 7, 14 and safety. Unadjusted and adjusted analysis will be carried out on OI, CRs, PF ratio, SOFA score, to test whether there is a statistically significant difference between the groups.

Unadjusted analysis will be carried out using Independent sample t-test. Adjusted analysis will be carried out using ANCOVA or [mixed modelling technique](#), based the number of data points available at each time point. Estimates & 95% confidence interval will be reported.

The number of AE, ARs, SAE, SARs, SUSARs and number (%) of patient experiencing the events will be reported. Fisher's exact test and proportion test will be used to check whether incidences of adverse events differ between the groups. Relative risk and 95% CI will be reported.

Exploratory analysis on mediators will be carried out using student t-tests or non-parametric alternative and Fishers Exact Test, presented by day where applicable. The estimates & 95% CIs will be reported. Statistical diagnostic methods will be used to check for violations of the assumptions, and transformations will be performed if required. For binary outcome measures, risk ratios and associated 95% CI will be calculated. Survival analysis technique will be used for time-to-event data. Median survival time & 95% CI will be estimated using Kaplan-Meier estimation method and the Kaplan-Meier plots will be presented. In all time-to-event analyses, patients that did not experience the event in question (e.g. death) were censored on the date last seen or 90 days. The equality of survivorship function of aspirin & placebo group will be tested

for significance using a log-rank  $\chi^2$  test. Hazard ratios (HRs) & 95% CIs will be reported if the proportionality assumption holds.

Correlations between changes in the biological markers measured and physiological and clinical outcomes will be assessed by appropriate graphical and statistical methods including Pearson's (or Spearman's) correlation coefficient.

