**Table A2. Treatment after Trial Entry**

	Aspirin N = <n>	Placebo N = <n>
Number of patients who received at least one dose of treatment	n	n
Duration of study drug (days)	xx.x ± x.x	xx.x ± x.x
Time from randomisation to start of study drug (hours)	xx.x (xx.x to xx.x)	xx.x (xx.x to xx.x)
Reasons for termination of study drug		
14 days after randomisation	n	n
Study drug related adverse event	n	n
Discharge from critical care	n	n
Death	n	n
Discontinuation of active medical treatment	n	n
Request for discontinuation of trial drug by patient or legal representative	n	n
Decision by a physician on safety grounds	n	n
Clinical indication for treatment with Aspirin	n	n
Other	n	n
Protocol deviations/ violations		
Eligibility	n (xx.x%)	n (xx.x%)
Study Drug Administration		
Did not receive allocated treatment a	n (xx.x%)	n (xx.x%)
Received treatment of other group b	n (xx.x%)	n (xx.x%)
Study drug omitted in error c	n (xx.x%)	n (xx.x%)
Study drug given in error	n (xx.x%)	n (xx.x%)
Other	n (xx.x%)	n (xx.x%)

Mean ± SD or Median (p25 to p75) presented for continuous variables and no. or no. (%) for all categorical variables a- Numbers based on study drug administration data, b- Numbers based on the randomisation listing held by trial Statistician, c- Numbers based on Protocol deviation data

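### SOFA at days 4, 7 and 14 is compared only among patients alive and in ICU that day, a group aspirin may itself change, with no stated handling of death or ICU discharge

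*SAP*

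**What the plan says.** SAP section 2.2 lists change in SOFA from baseline to days 4, 7 and 14 as a secondary outcome. On when measurement ends, the same section says: "Outcomes will be measured at baseline and daily up to day 14 or until the patient is discharged from ICU or the patient dies".

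On missing values, section 3.4 says: "If any data is missing imputation will not be done". Section 6 makes one exception, for the primary outcome: "Secondary analysis will be carried out, if the day 7 OI values are missing, using last value carry forward method". Section 7.4 repeats a last-available-value fallback in the day-7 OI line only, and Table A3 has an imputed row only for day-7 OI. The SOFA line and the SOFA rows have no fallback, only an n for each day.

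Section 6 tests SOFA between arms by t-test and by ANCOVA or a mixed model, the choice depending on how many data points exist. It also states that analyses follow the intention-to-treat principle. Table A2 counts "Discharge from critical care" and death among the reasons for ending study drug, so the plan expects both. For the SOFA score, section 4 refers to a separate guideline that is not reproduced.

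**The concern.** Taken together, these rules limit the SOFA comparison on a given day to patients alive and in ICU that day. Deaths, the worst organ-failure outcomes, drop out. So do live ICU discharges, which are generally among the best. Both events happen after randomisation and both may respond to aspirin, so the two arms can be selected differently.

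The plan recognises the problem elsewhere. Section 2.1 chooses day 7 for OI to limit competition from death and extubation, and section 4 sets ventilator-free days to zero for patients who die within 28 days. SOFA runs to day 14, where losses can only be larger, and has neither protection. OI depends on ventilator settings, so a gap after extubation is partly unavoidable there. Death and live discharge, by contrast, can be placed at the two ends of an organ-failure scale.

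At stake is one of the few efficacy signals in a phase 2 trial: a real effect may be diluted, or the estimated difference may change sign.

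**Working it through.** **The plan's own figures.** The SAP states no sample size, rate or SD for SOFA. Its only calculation is for OI: difference 39, SD 51, two-sided 0.05, 80% power. The two-sample t-test gives 27.8, so 28 per arm (power 80.2%). Then 56/0.95 = 58.9, so 59, rounded to 60 for equal arms. This reproduces section 5. The 5% allowance is for withdrawal and loss to follow-up, not for death or ICU discharge, so it gives SOFA no cover.

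**Assumptions.** Every rate and SOFA value below is mine. Differences are aspirin minus placebo, and negative favours aspirin.

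**(a) Deaths prevented, by hand.** Assume placebo deaths of 20% halved by aspirin, 15% discharged in both arms, a change of −2 in patients who stay, and +1 in those saved.
- Placebo, scored patients: −2.
- Aspirin, scored patients: (0.65 × −2 + 0.10 × 1)/0.75 = −1.60.
- Observed difference: **+0.40**, against aspirin.
- All randomised, with death scored 24 from a baseline of 10 (change +14) and discharge at −6. Placebo: 0.65 × −2 + 0.20 × 14 + 0.15 × −6 = 0.60. Aspirin: 0.65 × −2 + 0.10 × 1 + 0.10 × 14 + 0.15 × −6 = −0.70. Difference: **−1.30**.

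With saved patients at 0 to +3, the observed difference is +0.12 to +0.31 for placebo deaths of 10%, +0.27 to +0.67 for 20%, and +0.43 to +1.07 for 30%. If saved patients improve like the others (−2), it is 0.

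**(b) Faster discharge, by hand.** Assume 15% dead and 15% discharged in both arms. A further 20% recover quickly: on aspirin they leave at −5, on placebo they are still in ICU at −4. The rest are at −2.
- Placebo, scored patients: (0.50 × −2 + 0.20 × −4)/0.70 = −2.57.
- Aspirin, scored patients: −2.
- Observed difference: **+0.57**. The difference among all survivors is 0.20 × −1/0.85 = −0.24.

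With 10 to 30% extra discharges at −4 to −6, the observed difference is +0.14 to +1.29.

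**(c) Simulation, 30 per arm.** SOFA = 8 + 3.6s + N(0, 1.5), so SD = √(3.6² + 1.5²) = 3.9. Death and discharge come from latent variables correlated +0.7 and −0.7 with severity s. The test is on raw SOFA among patients alive and in ICU. In the first four rows SOFA is identical in both arms, so the correct difference is 0.

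| Scenario (placebo v aspirin) | Observed difference |
|---|---|
| Assumed day 4: deaths 10% v 5%, discharge 5% both | +0.20 |
| Assumed day 7: deaths 20% v 10%, discharge 10% both | +0.39 |
| Assumed day 14: deaths 30% v 15%, discharge 30% both | about +0.5 |
| Assumed day 14: deaths 30% v 15%, discharge 20% v 40% | about +1.2 |
| Aspirin lowers severity by 1 point, which also drives death and discharge (30% each on placebo) | about −0.55 |
| The same, 2 points | about −1.1 |

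- With 30% for both events in both arms and no effect, about 13 of 30 per arm are analysed. The t-test and the ranked test each reject in about 5% of trials.
- In the fourth row the t-test rejects in about 18% of trials, almost all against aspirin. A rank test with death worst and discharge best rejects in about 29%, in aspirin's favour.
- In the last row the rank test rejects in about 37% of trials, against 16% for the t-test.

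**(d) Stricter selection.** If the worst patients on the SOFA-change scale always die and the best always leave (10 to 30% each on placebo), a uniform benefit of 1 to 2 points shows as −0.09 to −0.85. That is dilution, not reversal on average, although the observed sign favours placebo in 7 to 40% of trials.

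**The case against.** A reader might infer that the plan will make an effective drug look harmful. The documents do not support that. The reversals in (c) need aspirin to change deaths or discharge while leaving organ failure untouched, which is an extreme. When aspirin lowers the severity behind all three, the estimate shrinks but keeps its sign on average, and significant results in the wrong direction occur in at most about 1% of trials. At the assumed day-4 and day-7 rates the shift is small against a standard error of about 1 point: wrong-direction rejection is about 4 to 5%, against about 2.4% under no effect. All of this stands.

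The simulation also tests raw SOFA by t-test, without a baseline, a change score or repeated measures. Table A4 shows a group-by-day mixed model, which would use earlier scores of patients who later leave and could reduce the discharge bias. That stands in part. The model is optional under section 6, it leaves the t-test unchanged, and it does not define a SOFA value after death.

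The SOFA guideline cited in section 4 might contain a rule for death or discharge. It cannot be checked here. The SAP does not say that it does, and sections 2.2 and 3.4 read otherwise.

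Finally, a ranked outcome mixes mortality and discharge with organ failure, and section 2.2 keeps mortality and ICU stay out of the major outcomes for lack of power. That is a sound reason not to replace the SOFA analysis. It does not argue against adding a second one. The n per day in Table A3 and the mortality and ICU-stay table give partial context, but not the numbers dead and discharged by days 4, 7 and 14.

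**Conclusion.** The point holds as a selection problem built into the stated rules. SOFA is tested at three days on patients alive and in ICU, a group defined after randomisation, under a heading of intention to treat. No visible section says how death or ICU discharge enters the comparison.

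The size cannot be read from the SAP, which gives no death or discharge rates. Under the assumptions above, a general benefit is roughly halved, and shrinks further under stricter selection. A benefit acting mainly through fewer deaths or faster discharge can appear as +0.2 to +0.4 points at day 4 or 7 and +0.5 to +1.2 at day 14. Reversal is possible, not expected. The weakness is greatest at day 14. It affects a secondary outcome and leaves the primary OI comparison untouched.

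**What to change.** In section 6 and Table A3:

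1. Keep the planned SOFA analysis, but label it as conditional on being alive and in ICU on that day.
2. For days 4, 7 and 14, show the numbers dead, discharged from ICU and assessed in each arm.
3. Add a prespecified analysis of all randomised patients, most needed at day 14. Rank death by that day worst, then in-ICU SOFA from high to low, then alive and discharged from ICU best. Compare arms by a rank or proportional-odds method adjusted for baseline SOFA.
4. State that the organ-failure conclusion rests on both analyses.

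The cost is a few sentences of SAP text and a little code. The dates of death and ICU discharge are already needed for the duration definitions in section 4. The drawback is one more analysis, whose effect is an odds ratio or win probability that mixes death and discharge with SOFA and is not in SOFA points.

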## **2.3 Exploratory analyses**

In order to determine the potential mechanism of action of aspirin, the study will investigate the biological effect of aspirin on pulmonary and systemic:

1. Inflammatory responses
2. Indices of epithelial and endothelial function and injury
3. Lipid inflammatory mediators

## **2.4 End of trial**

The trial will end when 60 patients have been recruited and completed 90-day follow-up.

The trial will be stopped prematurely if:

- Mandated by the Ethics Committee
- Mandated by the MHRA
- Mandated by the sponsor e.g. following recommendations from the DMEC

# **3. DATA**

## **3.1 CRF Forms and variables**

Full details of data collection and timing are described in the trial protocol (version 3, 20/07/2015). A copy of the CRF is presented in the Trial Master File.

## **3.2 Management of datasets**

Below is the standard policy for management of data in the CTU as given in the CTU SOPs, at the time of analysis (including DMEC reports/Interim analysis (if required)):

The trial database will be stored in MACRO:

DMEC reports: - In collaboration with the Statistician, the Data Manager will create MACRO output files to support the analysis. This will act as the frozen dataset. It is the responsibility of the statistician to accurately record the date of freezing and ensure all data is retrieved. If there are no errors, the study database will be re-opened for further data entry.

If there are errors, the Study Statistician will report these to the Data Manager. The Data Manager in consultation with the Study Statistician, Data Project Manager and Senior Study Statistician will resolve the errors and determine which of the database closure activities are required to be undertaken. The Data Manager will re-create the MACRO output files to support the analysis.

Database closure & lock: The same process for DMEC reporting will be followed for database closure and lock, the only difference being when the MACRO output files are created and there are no errors found for final analysis, the database should be locked as per Section 4.2 SOP DM09.

### 3.3 Data completion schedule

The following table describes the time points for completion of clinical record forms.

**Table.1. Data Completion Schedule**

CRF	Day									
	0	1	2-3	4	5-6	7	8-13	14	15- 42	90
Eligibility assessment	X									
Informed consent	X									
Randomisation	X									
Baseline data	X									
Daily data		X	X	X	X	X	X	X		
Study drug administration		X	X	X	X	X	X	X		
Adverse events		X	X	X	X	X	X	X	X	
BAL sampling	X			X						
Blood sampling	X			X		X		X		
Urine sampling	X			X		X		X		
Clinical Outcome									X	X

### 3.4 Data verification

Data verification, consistency and range checks will have been performed at the data entry stage by the CTU, as well as checks for missing data (copies can be found in the Trial Master File). Additional range, consistency and missing data checks will be performed, as appropriate, when the analysis is performed (and when the datasets for analysis are constructed). All variables will be examined for unusual, outlying, unlabelled or inconsistent values.

Given the thorough nature of our follow-up procedure we expect the issue of missing data to be relatively minimal. We anticipate high compliance with initial data collection as this is close to the time of patient registration. If any data is missing imputation will not be done.

Any problems with trial data will be queried with the Trial Managers, Data Managers, or statisticians, as appropriate. If possible, data queries will be resolved, although it is accepted that due to administrative reasons and data availability a small number of problems will continue to exist. This will be minimised.

### 3.5 Data coding

The variable codings will be as specified on the CRF.

## 4. DEFINITION OF TERMS

Term	Definition
Vasopressors	Vasopressors are defined as any inotropic/vasopressor agent except dopamine < 6mcg/kg/min.
SAP II	New Simplified Acute Physiology Score
Murray Lung Injury Score	Scoring system using radiology, PF ratio, PEEP and respiratory compliance to assess the extent of adult lung injury.
APACHE II score	Acute Physiology and Chronic Health Evaluation II score. A disease severity classification system.
Predicted Body Weight (Kg)	$PredictedBodyWeight = \begin{cases} 50 + 0.91 * (Height - 152.4) & \text{for Male} \\ 45.5 + 0.91 * (Height - 152.4) & \text{for Female} \end{cases}$
Oxygenation Index (cmH 2 O/kPa)	$OI = \frac{(MAP * FiO_2)}{PaO_2} * 100$
Total SOFA Score	Guideline 13: SOFA Score v1.0 Final 04/02/2016
Respiratory Compliance (ml/cmH 2 O)	$RespiratoryCompliance = \frac{TidalVolume}{[PlateauPressure - PEEP]}$
PF ratio (kPa)	$PFRatio = \frac{PaO_2}{FiO_2}$
Unassisted breathing	Unassisted breathing is defined as; extubated with supplemental oxygen, or room air, or open T-tube breathing, or tracheostomy mask breathing, or CPAP ≤ 5 cm H 2 O without pressure support for a calendar day. Patients receiving pressure support via non-invasive ventilation will be defined as

	receiving ventilatory support. The date recorded will be the first calendar day of the final period of ventilation free days
Ventilator free days (VFDs)	
The number of days alive and free from ventilation between final successful weaning and day 28 after study enrolment.
 $VFD = \begin{cases} (28 - x), & \text{if patient alive at day 28} \wedge x \leq 27 \\ 0, & \text{if patient died within 28 days} \vee x > 27 \end{cases}$ 
Where x is number of days until patient achieved unassisted breathing

Duration of ventilation (days)	
Duration of ventilation
 $= \begin{cases} \text{Date of unassisted breathing} - \text{Date of randomisation, if the patient achieved unassisted breathing} \\ \text{Date of death} - \text{Date of randomisation, if the patient died prior} \end{cases}$ 
This calculation will be censored at day 90.

Duration of ICU stay (days)	
Duration of ICU stay
 $= \begin{cases} \text{Date of first ICU discharge} - \text{Date of randomisation, if the patient is alive at ICU discharge} \\ \text{Date of death} - \text{Date of randomisation, if the patient died prior} \end{cases}$ 
Discharge from critical care is defined as discharge to a medical ward in the hospital or another hospital, A transfer between ICUs is not considered as a discharge from critical care. This calculation will be censored at day 90.

Duration of hospital stay (days)	
Duration of hospital stay
 $= \begin{cases} \text{Date of first hospital discharge} - \text{Date of randomisation, if the patient is alive at hospital discharge} \\ \text{Date of death} - \text{Date of randomisation, if the patient died prior} \end{cases}$ 
Hospital discharge is the first date that the patient is discharged to home/community, a transfer between hospitals is not considered as a hospital discharge. This calculation will be censored at day 90.

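### The day-28 ventilator-free-day score is taken from a final-weaning date with no day-28 limit, so re-ventilation after day 28 can turn a score of 22 into 0

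*SAP*

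**What the plan says.** Three adjoining entries in SAP section 4 (Definition of terms) are linked.

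- **Unassisted breathing.** After listing what counts as unassisted, the entry says which date is kept: "The date recorded will be the first calendar day of the final period of ventilation free days". It attaches no time window to that final period.
- **Ventilator free days.** In prose, the outcome is "The number of days alive and free from ventilation between final successful weaning and day 28 after study enrolment". The formula gives 28 - x if the patient is alive at day 28 and x is at most 27, and 0 if the patient died within 28 days or x exceeds 27. It then defines x: "Where x is number of days until patient achieved unassisted breathing". That is the term defined in the entry just before.
- **Duration of ventilation.** For patients who reach unassisted breathing, this is the same date minus the randomisation date, with the rule "This calculation will be censored at day 90".

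Section 2.2 names the outcome among those recorded, "ventilation free days at day 28 and 28 and 90-day mortality", and says that the trial is too small for these to be major outcome measures. Table A 6 in Appendix 1 (survival, ventilation and length of stay) nevertheless shows VFDs by arm as mean and SD with a p-value.

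**The concern.** A score for the first 28 days should depend only on those 28 days. Here its one input is a date defined by the last weaning, with no limit on when that weaning may occur. The only time limit near that date is day 90, in the duration entry. An episode of ventilation after day 28 can therefore replace an early weaning date with a late one and push x past 27. The patient then receives the lowest score, the one given for death.

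If only one date is kept, the right score cannot be recovered from it afterwards. The analyst would have to return to the notes and decide case by case, in a 60-patient trial, which period to count. That decision belongs in the plan, before the allocation is known.

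**Working it through.** The SAP gives no expected VFD value, so there is no figure of the plan's own to reproduce. The check applies the section 4 definitions as written.

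**Inputs**
- x = days from randomisation to the first day of the final ventilation-free period (section 4, unassisted breathing and VFD entries).
- VFD = 28 - x if alive at day 28 and x ≤ 27; otherwise 0 (section 4).
- Planned arm size: 30 (section 5).
- Rate of re-ventilation after day 28: not given.

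**Step 1: one patient, same first 28 days.** The patient is alive at day 28 and ventilation-free from day 6 through day 28.

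| After day 28 | Recorded date gives x | VFD |
|---|---|---|
| Not re-ventilated | 6 | 28 - 6 = 22 |
| Re-ventilated day 30, weaned day 33 | 33 | 0 |
| Re-ventilated days 35 to 38, weaned day 39 | 39 | 0 |
| Re-ventilated day 85, weaned day 89 | 89 | 0 |

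The last three rows differ from the first only in what happens after day 28.

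**Step 2: the formula inside the window.** For a patient re-ventilated on day 20 and weaned on day 24, x = 24 and VFD = 28 - 24 = 4. At the boundary, x = 27 gives 1 and x = 28 gives 0. The formula behaves sensibly when the final weaning falls within 28 days. The fault is only that x has no such limit.

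**Step 3: a case the text leaves open.** Suppose the patient is re-ventilated after day 28 and never weaned again. The last ventilation-free period may still be the one from day 6 (score 22), or final weaning may be treated as not achieved (score 0). The SAP does not settle this.

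**Step 4: effect on an arm mean.** The loss per affected patient is 28 - x, with x the weaning date that stood at day 28.
- In the example: 22/30 = 0.73 days.
- For weaning dates from day 1 to day 27: from 27/30 = 0.90 down to 1/30 = 0.03 days.
- No affected patient in the arm: 0. Two like the example: 44/30 = 1.47 days.

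These are shifts in one arm. If both arms have the same number of such patients with the same loss, the between-arm difference does not change. With one in one arm and two in the other, it changes by 0.73 days.

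**The case against.** The strongest reply is that the prose already closes the interval at day 28, and section 2.2 names the outcome as a day-28 quantity. An ordinary reader could take the final weaning to mean the final one by day 28, which gives the example patient 22. That reading is available. However, the prose does not state it, and the formula takes x from a term whose own entry has no window. Two readings of one patient, 22 and 0, remain open.

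A second reply concerns data capture. Daily data stop at day 14 (section 3.3), ICU stay uses the first discharge, and section 3.1 leaves collection details to the protocol and CRF, which are not at hand. A short re-ventilation in week five might never update the date. This stands as a limit: tracking to day 90 is inferred from the censoring rule for duration and is not stated for the date itself.

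Some stronger readings are tempting but not supported:

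- *Every patient re-ventilated after day 28 scores 0.* The 0 follows only if the patient is weaned again (step 3).
- *The rule biases the treatment comparison.* Only patients alive after day 28 can be affected, so exposure could differ by arm. But a survivor scored 0 scores no lower than if that patient had died, and no document gives a rate. The effect on the difference may be nil.
- *Duration of ventilation is also wrong, because the example gives 39 days against about 6 + 4 = 10 days on the ventilator.* Elapsed time to final unassisted breathing is a stated and usable definition. Preferring ventilated days is a choice, not a correction.

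**Conclusion.** The point holds as a minor defect in a definition. As written, x in a 28-day score comes from a date that can fall after day 28, and a patient weaned again after late re-ventilation scores 0 instead of 22 in the example. The conclusion rests on reading the final period literally and on the inference, from the day-90 censoring of duration, that the date can be updated after day 28.

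The size is small: 0.73 days in one arm's mean per patient like the example, for a number of patients that is unknown and may be zero. VFDs are outside the primary and listed secondary outcomes, and neither the primary analysis nor the sample size is touched. It is still worth settling before unblinding, because VFDs are compared between arms with a p-value.

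**What to change.** In section 4, add to the VFD entry that:

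1. x is the number of days to the first day of the ventilation-free period in progress at day 28;
2. a patient still ventilated on day 28 scores 0;
3. ventilation that starts after day 28 is ignored.

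Where this date differs from the one used for duration of ventilation, record both.

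The words *in progress at day 28* matter. A rule based on the last weaning on or before day 28 would give 22 to a patient weaned on day 6, re-ventilated on day 25 and still ventilated on day 28. The three statements give that patient 0. They also settle the case of a patient re-ventilated after day 28 and never weaned again, who keeps the day-28 score.

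The cost is a short addition to section 4 and one extra date for the few patients re-ventilated after day 28. The duration-of-ventilation definition can stay as it is.
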